3.0 OBJECTIVES AND ENDPOINTS

Table 3 Study Objectives and Endpoints

Objectives	Endpoints
Primary	

 • To evaluate the safety and reactogenicity profile of GSK Vaccines Institute for Global Health (GVGH) invasive nontyphoidal Salmonella-typhoid conjugate vaccine (iNTS-TCV) vaccine in healthy European/African adults 	
 • Number of participants in Europe/Stage 1 with solicited administration site and systemic events during 7 days after each study intervention administration (ie, on the day of study intervention administration and the 6 subsequent days) occurring at Day 1, Day 57, and Day 169, by study intervention group • Number of participants in Europe/Stage 1 with unsolicited adverse events (AEs) during 28 days after each study intervention administration (ie, on the day of study intervention administration and the 27 subsequent days) occurring at Day 1, Day 57, and Day 169, by study intervention group • Number of participants in Europe/Stage 1 with serious adverse events (SAEs) from first study intervention administration (Day 1) to 28 days after third study intervention administration (Day 197), by study intervention group • Number of participants in Europe/Stage 1 with AEs/SAEs leading to withdrawal from the study and/or withholding doses of study intervention, from first study intervention administration up to 28 days after third study intervention administration (Day 1 to Day 197), by study intervention group • Number of participants in Europe/Stage 1 with deviations from normal or baseline values for hematological, renal, and hepatic panels test results at 7 days after each study intervention administration (Day 8, Day 64, and Day 176) and at 28 days after each study intervention administration (Day 29, Day 85, and Day 197), by study intervention group • Number of participants in Africa/Stage 2 with solicited administration site and systemic events during 7 days after each study intervention administration (ie, on the day of study intervention administration and the 6 subsequent days) occurring at Day 1, Day 57, and Day 169, by study intervention group • Number of participants in Africa/Stage 2 with unsolicited AEs during 28 days after each study intervention administration (ie, on the day of study intervention administration and the 27 subsequent days) occurring at Day 1, Day 57, and Day 169, by study intervention group • Number of participants in Africa/Stage 2 with SAEs from first study intervention administration (Day 1) to 28 days after third study intervention administration (Day 197), by study intervention group • Number of participants in Africa/Stage 2 with AEs/SAEs leading to withdrawal from the study and/or withholding doses of study intervention, from first study intervention administration up to 28 days after third study intervention administration (Day 1 to Day 197), by study intervention group

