9.4.1 Primary Endpoints

The analysis on primary objective will be based on the Solicited, Unsolicited, and Exposed Sets, as indicated in [Table 11](#).

Table 11 Primary Endpoints-Statistical Analyses

Endpoint	Statistical Analysis Methods
Primary safety	
 The number and percentage of participants with at least 1 solicited administration site and systemic event during the 7-day follow-up period will be tabulated by group after each study intervention administration and overall. The same calculations will be performed for symptoms rated as Grade 3. The number and percentage of participants with at least 1 unsolicited adverse event (AE) during the 28-day follow-up period will be tabulated by group after each study intervention administration and overall. The same calculations will be performed for symptoms rated as Grade 3. The percentage of doses associated with at least 1 solicited administration site and systemic event during the 7-day follow-up period will be tabulated for the overall administration course. The same calculations will be performed for symptoms rated as Grade 3. The percentage of doses associated with at least 1 unsolicited AE during the 28-day follow-up period will be tabulated for the overall administration course. The same calculations will be performed for symptoms rated as Grade 3. The number and percentage of participants reporting each individual solicited administration site (ie, injection site pain, erythema [redness], swelling) and systemic event (ie, fever [$\geq 38.0^{\circ}\text{C}$], headache, myalgia, arthralgia, fatigue; any Grade and Grade 3) during the 7-day solicited follow-up period after each study intervention administration and by group will be tabulated. The percentage of doses associated with each individual solicited administration site and systemic event will be tabulated for the overall administration course. Occurrence of fever will be reported as number and percentages of participants reporting temperature $\geq 38^{\circ}\text{C}$ in 0.5°C cumulative increments during the 7-day follow-up period. This will be tabulated for each group after each dose. The number and percentage of participants with at least 1 reported unsolicited AE during the 28-day follow-up period after each study intervention administration and by group, as classified by the Medical Dictionary for Regulatory Activities (MedDRA) preferred term, by system organ class and by group will be tabulated. The same tabulation will be performed for Grade 3 unsolicited AEs and for unsolicited AEs according to relationship to study intervention administration. The number and percentage of participants reporting serious AEs (SAEs) and AEs/SAEs leading to withdrawal from the study and/or withholding doses of study intervention, collected from first study intervention administration up to 28 days after third study intervention administration (Day 1 to Day 197) will be tabulated. The detailed listings will also be produced. For each group, for hematological, renal, and hepatic panel test results at 7 days after each study intervention administration (Day 8, Day 64, and Day 176) and at 28 days after each study intervention administration (Day 29, Day 85, and Day 197), and for other tests at baseline: 
 The percentage of participants having hematological, renal, and hepatic results below or above the laboratory normal ranges will be tabulated by time point.

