Document: \\dccar2dnetvnasc01p-lan1.quintiles.net\cp_ops\PROJECTS\Glaxo SmithKline\GSK216152_WZA10802\SAP
Author: PPD Version Number: 2.0
Version Date: 07DEC2023

Template No: CS_TP_BS016 – Revision 7
Effective Date: 01Nov2021

Reference: CS_WI_BS005

In Stage 2 (Africa), a total of 105 healthy African adults, randomized in a 3:3:1 ratio, will receive:

- The full dose of the candidate iNTS-TCV vaccine and concomitant saline to be administered in different arms (Study Group 7), or
- Separate administration of full doses of iNTS-GMMA and TCV vaccines in different arms (Study Group 8), or
- MenACWY (Menveo) and saline for the first administration, TdaP (Boostrix) and saline for the second administration and Typhoid Vi polysaccharide vaccine (Typhim Vi) and saline for the third administration in different arms (Study Group 9). This is the Control_Stage 2 Group.

The first 21 participants in Stage 2 will initially be recruited with administration proceeding sequentially, at least 60 minutes apart. All safety data from these participants up to 7 days after the first administration of the study intervention will be reviewed by the iSRC and the recruitment of the remaining 84 participants in Stage 2 will only commence if there is a positive evaluation by the iSRC. The study interventions will be administered in parallel in the remaining 84 participants.

All 155 participants (Stage 1 and Stage 2) will be closely observed for a minimum of 60 minutes after each study intervention administration, before leaving the facilities. The Investigator will decide if the participant should be observed for more than 60 minutes after each study intervention administered, if required.

An internal GSK Safety Review Team (SRT) and iSRC will also be involved in the safety oversight for this study. For all planned safety data reviews refer to Table 14 and 15 of the study protocol.

The trial will be conducted in 2 sites, each with a different Principal Investigator. A total of 155 participants are planned to be randomized to achieve at least 133 evaluable participants. Each participant will be part of this trial for approximately 13 months (from the Screening starting 28 days before first study intervention administration and until 6 months after third study intervention administration).

Document: \\dccar2dnetvnasc01p-lan1.quintiles.net\cp_ops\PROJECTS\Glaxo SmithKline\GSK216152_WZA10802\SAP
Author: PPD Version Number: 2.0
Version Date: 07DEC2023

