3.3. CHANGES TO ANALYSIS FROM PROTOCOL

Entered Set is defined in Section 5 to comprise of participants who provide informed consent for the

Document: \\dccar2dnetvnasc01p-lan1.quintiles.net\cp_ops\PROJECTS\Glaxo SmithKline\GSK216152_WZA10802\SAP
 Author: PPD Version Number: 2.0
 Version Date: 07DEC2023

Template No: CS_TP_BS016 – Revision 7
 Effective Date: 01Nov2021

Reference: CS_WI_BS005

study.

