The analysis of unsolicited adverse event will be performed in the Unsolicited Safety Set. The verbatim reports of unsolicited symptoms will be reviewed by a physician and the signs and symptoms will be coded per the Medical Dictionary for Regulatory Activities (MedDRA), Version 26.0 or higher. Every verbatim term will be matched with the appropriate preferred term (PT). The percentage of participants with unsolicited AEs within 28 days after any doses with its exact 95% CI will be tabulated by group, stage and by MedDRA preferred term. Similar tabulation will be done for Grade 3 unsolicited AEs, for unsolicited AEs that resulted in a medically attended visit, for Grade 3 and causally related unsolicited AEs and for unsolicited AEs causally related to vaccination. These tabulations will include System Organ Class (SOC) and SOC/PT analyses.

The number of participants who experienced at least 1 SAE within 28 days after any dose, from dose 1 until 28 days post last dose (Day 197) and from Day 198 until Day 337 will be reported by treatment.

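### SAP 16.1 plans the unsolicited-AE tables only over any dose, while the primary endpoint and protocol Table 11 call for them after each administration, and the change is not declared

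*SAP*

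**What the plan says.** **Protocol, Section 3.0 (Table 3).** The primary unsolicited-AE endpoint for Stage 1 is: "Number of participants in Europe/Stage 1 with unsolicited adverse events (AEs) during 28 days after each study intervention administration", for the administrations at Day 1, Day 57 and Day 169, by group. Stage 2 has the same endpoint.

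**Protocol, Section 9.4.1 (Table 11).** Two rows apply.
- The count of participants with at least one event: "unsolicited adverse event (AE) during the 28-day follow-up period will be tabulated by group after each study intervention administration and overall". It is repeated for Grade 3.
- The MedDRA preferred-term (PT) and system-organ-class (SOC) table, for participants with "at least 1 reported unsolicited AE during the 28-day follow-up period after each study intervention administration and by group". It is repeated for Grade 3 and by relationship to the study intervention.

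**SAP, Section 16.1.** The unsolicited paragraph says: "The percentage of participants with unsolicited AEs within 28 days after any doses with its exact 95% CI will be tabulated by group", by stage and by PT, with SOC and SOC/PT versions. It goes on: "Similar tabulation will be done for Grade 3 unsolicited AEs, for unsolicited AEs that resulted in a medically attended visit", and then for related and for Grade 3 related events. It mentions no individual dose.

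**SAP, Section 3.3.** The only declared change from protocol is a new analysis set: "Entered Set is defined in Section 5 to comprise of participants who provide informed consent for the" study.

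**SAP, Section 3.1.** The Stage 2 control group receives a different active vaccine each time: "MenACWY (Menveo) and saline for the first administration, TdaP (Boostrix) and saline for the second administration and Typhoid Vi polysaccharide vaccine" (Typhim Vi) with saline for the third.

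**The concern.** Safety is the primary objective of a trial that gives this vaccine to humans for the first time. Protocol 4.2 says that testing three doses in adults is meant to allow the same number of doses to be tested in young infants. Whether unsolicited events become more or less frequent with repeat dosing is therefore a question the primary endpoint is built to answer, and a single any-dose percentage does not answer it.

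The Stage 2 control group adds a second difficulty. Its product changes at every administration, so an any-dose percentage cannot show whether Menveo, Boostrix or Typhim Vi preceded an event. Without per-dose rows beside it, the candidate vaccine cannot be read against the control dose by dose.

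**Working it through.** There is no sample size, power or error rate to reproduce. The check is a comparison of texts, followed by an illustration of what the any-dose summary loses.

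**1. Texts side by side**

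| Output | Protocol Table 11 | SAP 16.1 |
|---|---|---|
| At least 1 unsolicited AE | each administration and overall | any dose |
| By PT and SOC | each administration | any dose |
| Grade 3 unsolicited | each administration | any dose |
| Related unsolicited | each administration | any dose |
| Medically attended; Grade 3 related | not requested | any dose |

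**2. Is the SAP wording merely loose?** Probably not. Where the SAP wants output by dose it says so: for the combined solicited and unsolicited table and for individual solicited symptoms (both in 16.1), and for concomitant medication (Section 13). The unsolicited paragraph has no such phrase.

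**3. Does another SAP output fill the gap?** The combined table in 16.1 is by vaccination, for any, administration-site and systemic events, with a Grade 3 repeat. It uses the Exposed Set and is there for public disclosure. For one dose, let S be the participants with a solicited event, U those with an unsolicited event and C those with either. Then max(S, U) ≤ C ≤ S + U, so C and S fix U only to the range from C − S to C. A participant with injection-site pain already counts in C, and an unsolicited event in the same person adds nothing. The percentage-of-doses outputs cover the whole vaccination course and are not split by dose. Neither output gives the endpoint.

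**4. Group sizes.** 105 participants at 3:3:1 gives 105 × 3/7 = 45, 45 and 105 × 1/7 = 15, as in protocol Table 4. One control participant is 1/15 = 6.7 percentage points.

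**5. Illustration with rates (assumed, doses independent).** Any-dose rate = 1 − (1 − p1)(1 − p2)(1 − p3).
- Rising, 5%, 10%, 25%: 1 − 0.95 × 0.90 × 0.75 = 35.9%.
- Falling, 25%, 10%, 5%: 1 − 0.75 × 0.90 × 0.95 = 35.9%.

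**6. Illustration with counts (assumed, each affected participant affected at one dose only; Clopper-Pearson 95% CI, the SAP's method)**

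| Group | Counts at doses 1/2/3 | Any dose | Dose 1 | Dose 2 | Dose 3 |
|---|---|---|---|---|---|
| Control, n = 15 | 2/2/2 | 40.0% (16.3–67.7) | 13.3% (1.7–40.5) | 13.3% (1.7–40.5) | 13.3% (1.7–40.5) |
| Control, n = 15 | 6/0/0 | 40.0% (16.3–67.7) | 40.0% (16.3–67.7) | 0% (0–21.8) | 0% (0–21.8) |
| Control, n = 15 | 0/2/4 | 40.0% (16.3–67.7) | 0% (0–21.8) | 13.3% (1.7–40.5) | 26.7% (7.8–55.1) |
| Investigational, n = 45 | 3/3/3 | 20.0% (9.6–34.6) | 6.7% (1.4–18.3) | 6.7% (1.4–18.3) | 6.7% (1.4–18.3) |
| Investigational, n = 45 | 0/2/7 | 20.0% (9.6–34.6) | 0% (0–7.9) | 4.4% (0.5–15.1) | 15.6% (6.5–29.5) |

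Within each group the any-dose column is identical while the per-dose columns differ.

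**The case against.** **The shells may settle it.** SAP Section 8 says that the table templates fix the format and content of the outputs, and they are not among the documents available here. They may already carry dose columns. SAP Section 1 also puts all primary objectives in scope, and nothing in the SAP expressly cancels the Table 11 tables. This stands: the finding is about what the SAP text requires, not about what will finally be produced.

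**A reader might infer that a dose trend would be invisible.** The documents do not support that. The combined table is by vaccination, solicited symptoms are shown at each dose, SAP 6.4.1 assigns every event to a dose, unsolicited listings are planned, and the safety committee's reviews are tied to particular doses. A trend in unsolicited events could be diluted or have to be worked out by hand, but it would not disappear.

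**A reader might also infer that any pooled control rate is an SAP error.** It is not. Protocol Table 4 defines the Stage 2 control as one group, and Table 11's own overall count pools the three vaccines. The shortfall is only that no per-dose rows stand beside it. It does not touch solicited events, and SAP Section 16 plans no statistical comparison between groups for safety unless specified.

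**Per-dose cells are imprecise.** Also true: 0/15 has an upper limit of 21.8%, and 2/15 runs from 1.7% to 40.5%. Such cells will seldom separate one control vaccine from another. That limits what the tables can show, but the protocol asks for them all the same.

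**Conclusion.** The mismatch is real and undeclared. Taken as written, SAP 16.1 does not deliver the primary unsolicited-AE endpoint as the protocol defines it. Dose trends, and the control vaccine that preceded an event, could be read only indirectly, from the combined table or from listings. This should be corrected before the analysis, but it does not threaten the trial: the data are collected and the dose attribution is defined.

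The conclusion rests on the SAP and protocol text alone and would shrink to a wording correction if the shells already have the per-dose tables. The documents state no AE rates, so every rate and count in the illustrations is an assumption. They show that one any-dose figure can hide different patterns, not how large any pattern will be in this trial.

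**What to change.** In SAP 16.1, state that the following are tabulated after each vaccination and overall, by group and stage, on the Unsolicited Safety Set, using the attribution rule in SAP 6.4.1:
- participants with at least one unsolicited AE, any grade and Grade 3;
- the SOC/PT tables for any, Grade 3 and related unsolicited AEs.

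Keep the any-dose tables as the overall column, and confirm that the table shells match. If the sponsor prefers any-dose tables only, SAP 3.3 should declare the change and give the reason.

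Two additions are optional because the protocol does not ask for them: a footnote naming the vaccine given to the Stage 2 control group at each dose, and per-dose versions of the medically attended and Grade 3 related tables.

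The cost is a short text change and some extra columns, with no new data. The drawback is longer tables with small, imprecise per-dose counts.

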16.1.1. ADVERSE EVENTS LEADING TO DISCONTINUATION FROM STUDY OR FROM TREATMENT

Adverse events leading to permanent discontinuation from study and leading to discontinuation of study vaccine but continued further study procedures (safety or immunogenicity) will be identified by using the variable pertaining to outcome the Adverse Events page of the (e)CRF, and listed, separately. AEs leading to discontinuation from treatment will be listed.

Document: \\dccar2dnetvnasc01p-lan1.quintiles.net\cp_ops\PROJECTS\Glaxo SmithKline\GSK216152_WZA10802\SAP
Author: PPD Version Number: 2.0
Version Date: 07DEC2023

Template No: CS_TP_BS016 – Revision 7
Effective Date: 01Nov2021

Reference: CS_WI_BS005

16.1.2. SERIOUS ADVERSE EVENTS

Serious adverse events (SAEs) are those events recorded as "Serious" on the Adverse Events page of the (e)CRF, and will be listed.

16.1.3. DERIVATION

Adverse Event	Intensity grade	Parameter
Redness/swelling at administration site (greatest surface diameter in mm)	0	<20 mm.
	1 (Mild)	≥20 to ≤50 mm.
	2 (Moderate)	>50 to ≤100 mm.
	3 (Severe)	>100 mm.
Temperature ^a	0	<38.0°C.
	1 (Mild)	≥38.0°C to <39°C.
	2 (Moderate)	≥39.0°C to ≤40.0°C.
	3 (Severe)	>40.0°C.

^aFever is defined as temperature ≥38.0°C/100.4°F

16.2. SAFETY LABORATORY EVALUATIONS

Laboratory results will be included in the reporting of this study for Hematology and Biochemistry. A list of laboratory assessments to be included in the outputs is included in Table 9 of the protocol.

For each group and for each haematology and biochemistry parameter:

- The percentage of participants having hematology and biochemistry results below/within/ above the local laboratory ranges versus baseline will be tabulated by treatment, timepoint and stage.
- The percentage of participants with hematology and biochemistry results by grade versus baseline will be tabulated by treatment, timepoint and stage.

16.2.1. GRADING FOR LABORATORY DATA

Grades will be based on local laboratory ranges and derived from Food and Drug Administration [FDA] Guidance to Industry “Toxicity Grading Scale for Healthy Adult and Adolescent Volunteers Enrolled in Preventive Vaccine Clinical Trials” in Stage 1 and from the Division of AIDS (DAIDS) Table for Grading the Severity of Adult and Pediatric Adverse Events in Stage 2 (refer to Table 19 and Table 20 in protocol). Laboratory parameters not included in the grading scale will not be graded.

16.3. VITAL SIGNS

The following Vital Signs measurements will be reported for this study:

- Resting systolic and diastolic blood Pressure (mmHg)
- Resting heart rate (bpm)
- Respiratory rate (breaths per minute)
- Temperature (°C)

Observed vital signs data will be summarized by treatment and time point.

16.4. COVID-19

Data collected on the COVID-19 infection assessment page from the eCRF will be presented in listings.

17. DATA NOT SUMMARIZED OR PRESENTED

The other variables not summarized or presented are:

- Comments

These variables will not be summarized or presented, but will be available in the clinical study database, SDTM and/or ADaM datasets.

Document: \\dccar2dnetvnasc01p-lan1.quintiles.net\cp_ops\PROJECTS\Glaxo SmithKline\GSK216152_WZA10802\SAP
Author: PPD Version Number: 2.0
Version Date: 07DEC2023

Template No: CS_TP_BS016 – Revision 7
Effective Date: 01Nov2021

Reference: CS_WI_BS005

